#### 3.2. Safety outcomes

A safety analysis will be performed on the reported adverse events, if any.

4. Study design

4.1. General description

This study is a mono-center, prospective, open-label phase 1 study, consisting of the treatment of a

single moderate or severe migraine attack (Grade 2 or 3) at home.

4.2. Experimental protocol

Patients will be recruited from the research site database and advertising and will be enrolled during a

visit at the research site.

Inclusion and exclusion criteria will be reviewed, and the eligible patients will be trained about the

practical use of the Cefaly® Abortive Program device (device handling, electrode placement, etc.).

Following that training, they will perform themselves a first 20-minute stimulation session to control their

ability to use appropriately the device and bear the feeling of the stimulation.

Recruited patients (who meet all of the study entry criteria) will be provided with study material and

documents for 2 months to be used on an outpatient basis as soon as they experience a moderate or

severe migraine headache (Grade 2 or 3).

The overall study flow is illustrated in Figure 1. During the different phases the investigator will monitor

adverse events (AE).

4.2.1. Recruitment phase

Patients contacted from the research site database and advertising will be screened during a visit at

the research site.

Patient will receive the information and consent documents and have to sign these documents before

study procedures are initiated. Then, the investigator will verify that the patient meets all the 6 inclusion

criteria and none of the 13 first exclusion criteria. If this is the case, the patient will be trained about the

practical use of the Cefaly® Abortive Program device (oral explanation, video and instruction sheet)

and will perform him/herself a first 20-minute training session to check his/her ability to use the device

appropriately and therefore that the last exclusion criteria is not met.

Screened patients meeting all inclusion criteria and none of the exclusion criteria are enrolled in the trial

and will receive the study material (Cefaly® Abortive Program device with accessories) to be used at

home to treat a single migraine attack and the related paper documents (diary and AE collecting

form). The investigator will explain to the patient how to fill in these documents.

The patient will complete a practice diary (paper) for a simulated migraine during the screening visit, to ensure that he/she fully comprehends the procedure. The investigator or study coordinator will then review the diary in detail with the patient.

#### 4.2.2. Acute treatment phase

During the 2 months following the screening visit, the patient will be instructed to treat a single qualifying migraine headache. A migraine headache is a qualifying migraine if all the following conditions are met:

- 1. The migraine headache severity is moderate or severe (Grade 2 or 3).
- 2. The migraine headache is associated with at least one of these migraine-associated symptoms: photophobia, phonophobia, nausea, vomiting.
- 3. The migraine headache started less than four hours ago or the patient woke up with migraine.
- 4. No other migraine headache or headache has occurred in the previous 48 hours.
- 5. The migraine headache is not already resolving on its own i.e. the pain is not already diminishing.
- 6. No acute anti-migraine medication has been taken since the beginning of the migraine headache.

In case of qualifying migraine, patient will have to apply the Cefaly® Abortive Program device for a complete treatment session of 2 hours as soon as the migraine headache is moderate or severe (Grade 2 or 3).

In his/her diary, the patient will note the headache pain severity on the following scale: 0 = no pain; 1 = mild pain; 2 = moderate pain; 3 = severe pain. The patient will note as well the migraine associated symptoms (photophobia, phonophobia, nausea, vomiting) and will specify which associated symptom is the most bothersome symptom (MBS). The patient will note this data just before the start of the Cefaly® Abortive Program (baseline data) and 2 hours after the beginning of the treatment session (normally just after removing the device and the electrode if the session ran correctly) (2-hour data), whatever the duration of the stimulation session. The patient will also have to record if any aura was associated with the qualifying migraine attack.

Devices will be programed for only 1 treatment session to be performed at home to treat the qualifying migraine.

The Cefaly® device will be programed with the following parameters (Abortive Program): square pulse current (100 Hz,  $250 \mu s$ ) at a linearly increasing intensity starting at 0 mA up to a maximum of 16 mA after 14 minutes, then remaining stable for the rest of the session (106 minutes).

Patients will be instructed to not take any acute anti-migraine medication during the acute treatment .

phase.

During the acute treatment phase, when the Cefaly® Abortive Program device stopped, it may not be

restarted. Duration, intensity and/or interruption will be recorded for each patient thanks to a built-in

electronic system in the device.

In any case, the patient will have to note the headache pain severity in his/her diary at 2 hours after the

beginning of the treatment session (2-hour data), whatever the duration of the stimulation session. The

patient will note as well the migraine associated symptoms.

In his/her AE collecting form, the patient will record any adverse event occurring during the treatment

phase and is instructed to notify the investigator immediately for any serious or severe adverse

experience with the stimulation.

A follow-up phone call can be performed by the investigator.

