#### 5.1. Inclusion criteria

The following inclusion criteria apply:

- 1) Age from 18 to 65 years on the day of signing the informed consent form
- 2) ≥ 1-year history of migraine with or without aura according the diagnostic criteria listed in ICHD-III beta (2013) section 1, migraine (8), with the exception of aura without headache, hemiplegic migraine and brainstem aura migraine
- 3) Migraine onset before the age of 50 years
- 4) Having between 2 and 8 moderate or severe migraine attacks (Grade 2 or 3) per month in each of the two months prior to screening
- 5) Patient understands the study procedures, alternative treatments available, and voluntarily agrees to participate in the study by giving written informed consent
- 6) Patient is able to read and understand the written information (instruction sheet, paper diary and AE collecting form)

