#### 6.5. Medication during the trial

Patients will be instructed to not take any acute anti-migraine medication during the acute treatment phase. After the 2 hours acute treatment phase, if the patient has moderate or severe migraine

headache pain (Grade 2 or 3), he/she is allowed to take his/her own anti-migraine rescue medication. Use of acute medication will be recorded by the patient on the diary for the 24 hours following the beginning of the treatment.

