# 7. Practical study modalities

# 7.1. Efficacy outcome measures

The treatment efficacy outcomes will be assessed based on the following clinical data.

- **Headache pain severity.** In order to evaluate the modification of pain severity from baseline to 2-hour and 24-hour time points, patients will be asked to note their headache pain intensity on the following scale: 0 = no pain; 1 = mild pain; 2 = moderate pain; 3 = severe pain.
- **Migraine associated symptoms**. The patient will also note the presence of migraine associated symptoms (photophobia, phonophobia, nausea, vomiting) and will specify which associated symptom is the most bothersome symptom (MBS).
- **Rescue medication intake**. The patient will also record whether he/she took ANY acute rescue medication during the 24 hours following the beginning of the e-TNS session.

The following table depicts when the different measures will be made:

	At baseline, i.e. just before the beginning of the e-TNS session	2 hours after the beginning of the e-TNS session	24 hours after the beginning of the e-TNS session
Headache pain severity	•	•	•
Migraine associated symptoms	•	•	•
Most bothersome migraine associated symptom (MBS)	•		
Rescue medication intake			•

All clinical data will be collected on a paper diary and AE collecting form.

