#### 8.2.3. Statistical analysis

Modified intention-to-treat (mITT) analysis

Patient data will be included in the mITT analysis if all the four following conditions are met:

- 1. The patient treated a qualifying migraine.
- 2. The patient applied the Cefaly® Abortive Program treatment during at least one minute\*.
- 3. The headache pain severity score **AND** the migraine associated symptom(s) at baseline were reported in the diary.
- 4. The headache pain severity score **OR** the migraine associated symptom(s) at 2 hours were reported in the diary.

Data provided by Colucid Pharmaceuticals, Inc. and available on the following website: https://globenewswire.com/news-release/2016/09/06/869611/0/en/CoLucid-Pharmaceuticals-Announces-Achievement-of-Both-Primary-and-Key-Secondary-Endpoints-in-the-SAMURAI-Phase-3-Pivotal-Trial-of-Lasmiditan-in-Migraine.html (consulted in May 2017).

\*If the patient stopped the 2-hour treatment session before its end for any reason, he/she is kept in the modified intention-to-treat (mITT) analysis if all the other conditions are met.

If the patient takes rescue medication between 2 hours and 24 hours after the beginning of the e-TNS session, the headache pain intensity and associated symptoms presence can be affected by the medication and the last value carried forward method (2-hour value carried forward method in this case) will be applied for the 24-hour time point headache pain severity and migraine associated symptoms.

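### Qualifying condition 6 looks back only to headache onset and earlier medication is not among the described diary items, so attacks medicated during aura or prodrome count towards the device's 2-hour rates

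*Combined protocol and SAP*

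**What the plan says.** Section 4.2.2 lists six conditions for a qualifying attack. Two bear on this point. Condition 4: "No other migraine headache or headache has occurred in the previous 48 hours". Condition 6: "No acute anti-migraine medication has been taken since the beginning of the migraine headache". The documents do not say which drugs count as acute anti-migraine medication.

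Inclusion criterion 2 (section 5.1) admits migraine with or without aura, apart from a few named subtypes. Section 4.2.2 has the patient record whether aura accompanied the treated attack.

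Section 4.2.2 also states: "Patients will be instructed to not take any acute anti-migraine medication during the acute treatment" phase. Section 6.5 describes that phase as lasting 2 hours.

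Medication recording begins with the session. Section 6.5: "Use of acute medication will be recorded by the patient on the diary for the 24 hours following the beginning of the treatment". Section 7.1 covers "ANY acute rescue medication during the 24 hours following the beginning of the e-TNS session", and its schedule has no medication entry at baseline. Section 4.2.3 describes the same 24 hours.

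In section 8.2.3 the first mITT condition is "The patient treated a qualifying migraine". The other three concern at least one minute of treatment and the reported baseline and 2-hour scores. None concerns medication before the session.

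**The concern.** Aura and prodrome can come before the headache. A patient who takes an acute drug then, and whose headache goes on to Grade 2 or 3, has not breached condition 6. If the other conditions hold, the attack qualifies and enters the mITT set. The same is true of an analgesic taken shortly before onset for a non-headache pain.

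The study has one open-label treatment and no concurrent control (section 4.1). If the earlier drug takes effect between baseline and 2 hours, the result is counted as device pain freedom or MBS freedom, the two primary outcomes. No other arm shares the drug effect, and no described diary item would let the analyst separate these attacks later.

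The undefined drug term adds a second difficulty. Patients apply condition 6 themselves at home. One patient may regard an antiemetic or a simple analgesic as disqualifying and another may not. Nausea and vomiting are two of the four symptoms that can be the MBS, so this ambiguity reaches the second primary outcome directly.

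**Working it through.** **1. The plan's own figure.** Section 8.2.1 gives 42 evaluable patients for 32.2% against 7.7%, with at least 80% power and 5% significance. The two-group formula, two-sided without continuity correction, has mean rate (0.077 + 0.322)/2 = 0.1995:

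n = [1.960 × √(2 × 0.1995 × 0.8005) + 0.842 × √(0.077 × 0.923 + 0.322 × 0.678)]² / 0.245² = 40.6, so 41 per group.

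With 42 per group the power is 81.4%. For loss, 42/(1 − 0.30) = 60. The figure is thus close to a per-group size for two groups, although this trial has one; that is a separate matter. Nothing in this point changes 42 or 60.

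**2. Does another provision close the gap?**
- Condition 4 looks back 48 hours, but for headaches. It makes a drug for an earlier headache unlikely. It does not reach a drug taken in the aura or prodrome of the present attack, or for another pain.
- Conditions 1 and 5 require Grade 2 or 3 pain that is not already easing. They remove attacks that the drug has aborted or is relieving at baseline, but not those where it has yet to act.
- The instruction against medication applies to the acute treatment phase. Section 4.2.2 opens with the two months after screening, whereas section 6.5 describes the phase as 2 hours; the two should be reconciled. On either reading it is an instruction and not a qualifying condition, so a breach before the session would not remove the attack from the mITT set.
- Aura is recorded, but no described item says whether it was medicated.

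**3. Illustration of size.** Let f be the fraction of analysed attacks that were pre-medicated and q their 2-hour pain freedom. Neither is in the documents; both are assumptions. If the device does no better than the 7.7% reference, the expected rate is

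7.7% + f × (q − 7.7%).

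Taking q = 32.2%, the plan's expected rate borrowed from a drug trial:
- f = 5%: 0.95 × 7.7 + 0.05 × 32.2 = 8.9%
- f = 10%: 0.90 × 7.7 + 0.10 × 32.2 = 10.2%
- f = 20%: 0.80 × 7.7 + 0.20 × 32.2 = 12.6%

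One responder in 42 is 1/42 = 2.4 points.

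The plan names no test of the primary outcome against 7.7%. For illustration, take an exact one-sample binomial test with an upper tail of at most 2.5%. With 42 patients it needs at least 8 responders, and its false-positive chance is 1.4% when f = 0. Each cell shows the expected rate, then the chance of 8 or more responders:

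| Assumed q | f = 5% | f = 10% | f = 20% |
|---|---|---|---|
| 20% | 8.3%; 2.1% | 8.9%; 3.1% | 10.2%; 5.8% |
| 32.2% | 8.9%; 3.0% | 10.2%; 5.8% | 12.6%; 15.2% |
| 45% | 9.6%; 4.3% | 11.4%; 10.0% | 15.2%; 30.0% |

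The effect is small if pre-medication is rare and becomes material at about 10-20% or more. The documents give no reference rate for MBS freedom, so no matching calculation is possible for that outcome.

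**The case against.** Five points can be made for the plan.

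- **Selection works against a large bias.** Attacks that the drug prevented or was already easing do not qualify. Those that remain reached Grade 2 or 3 despite the drug and may respond at well below 32.2%. The formula gives an upward shift only if q exceeds the background rate. This stands: upward is the likely direction but not a certain one.
- **The illustrated shift is small.** At q = 32.2%, 5-10% pre-medication adds 1.2 to 2.5 points against a planned gap of 32.2 − 7.7 = 24.5 points. This also stands, subject to f being unknown.
- **Drugs taken earlier in the day are largely covered.** A reader might infer that any drug taken that day slips through. Condition 4 makes intake for an earlier headache unlikely, so what remains is intake in aura or prodrome, or for a non-headache reason.
- **The gap in the data may be partly recoverable.** The diary and CRF forms are not in the documents, and the section 7.1 schedule is not a full inventory, since it omits aura. Sections 4.2.4 and 8.1 provide for diary review and queries, and the aura record allows a subgroup to be examined. But every passage that describes medication recording starts it at the session, and the aura record does not show who took a drug.
- **This is an open pilot.** Section 1 presents it as preparation for a controlled trial. The lack of a control is a known limit, but that makes clean attack qualification more useful.

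**Conclusion.** The concern holds in a limited form. The text of condition 6 admits attacks medicated before headache onset, the mITT rules do not remove them, and the described diary items do not identify them. With no control, any later drug effect would be credited to the device in both primary outcomes, probably upward. The size cannot be computed from the documents. The shift from 7.7% to 8.9-10.2% rests on an assumed 5-10% frequency and an assumed 32.2% response in these attacks.

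Two stronger readings are not supported. A reader might infer that the plan lets antiemetics through. It does not say so: the term is undefined, and an antiemetic taken for the attack could equally be read as disqualifying. That is an ambiguity to resolve, not a stated allowance. A reader might also infer that the primary rates are bound to be materially inflated. That would need a pre-medication frequency and a response rate for these attacks, and the documents give neither.

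**What to change.** For attack qualification and mITT condition 1:
- Start the condition 6 window at the first sign of the attack, aura included. Any further look-back is for the sponsor to set; the documents give no basis for a particular length.
- Define which drug classes count, stating explicitly the status of antiemetics and simple analgesics.
- Reconcile sections 4.2.2 and 6.5 on what the acute treatment phase covers.

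For data and analysis:
- Add a baseline diary line for any acute drug taken before the session, with clock time.
- List every pre-medicated attack, including those that lose qualifying status.
- Prespecify a sensitivity analysis of both primary outcomes without any attack that has a recorded pre-session drug. This also covers drugs outside the reworded window or the defined classes.

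The cost is one reworded condition, one definition, one diary line and one extra analysis. The sample size stays as it is. The main downside is that the device is programmed for a single home session, so a patient who uses it on a pre-medicated attack is lost from the mITT set. The rule should therefore be covered in the screening-visit training and practice diary. These changes settle which attacks are analysed and leave what patients may take unchanged.

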4.2.3. Post-treatment phase

Two hours after the beginning of the treatment session, the patient is allowed to take rescue medication

if the migraine headache pain is still moderate or severe, or if after initial pain relief (no headache or

mild headache pain) a moderate or severe headache is resuming.

The patient will have to note the headache pain severity in his/her diary at 24 hours after the beginning

of the treatment session (24-hour data), as well as the migraine associated symptoms. Patients will also

be instructed to record in their diary the rescue medication intake, if any, during the 24 hours following

the beginning of the treatment session.

In his/her AE collecting form, the patient will record any adverse event occurring during the 24 hours

following the beginning of the treatment and is instructed to notify the investigator immediately for any

serious or severe adverse experience with the stimulation.

4.2.4. Final visit

The patient will be instructed to return to the study site within approximately 4 days after the treatment

session to return the study material as well as completed diary and AE collecting form. The investigator

will review the paper diary in detail to ensure data accuracy (to avoid any missing data, unclear data

or discrepancies). If necessary, the investigator will instruct the patient to make him/herself corrections

and to sign the corrections with his/her screening number and the date (no initials).

All adverse events reported on the AE collecting form will be reviewed by the investigator to assess

severity. Additionally, the investigator will ask the patient if he/she has experienced any adverse effect

not reported on the form.

4.2.5. Discontinuation

**Withdrawal** 

Patients may withdraw their consent at anytime during the study. If a patient wishes to discontinue from the study but no discontinuation visit is performed (e.g., patient refuses to return to the study site), then the patient should be formally discontinued from the study on the day the decision to discontinue is

made.

Lost to follow-up

All attempts must be made to contact a patient who is lost to follow-up. Patients who are lost to follow-up should be formally discontinued from the study on the day of the last unsuccessful attempt at

contact.

Absence of qualifying migraine

If a patient has not treated a qualifying migraine attack within two months of the screening visit, he/she will be discontinued from the study and study material will have to be returned to the study site.

Notification and practical modalities

At a minimum, for any patient who discontinues the study, the patient status must be completed in the CRF. When a patient discontinues prior to study completion, all applicable activities scheduled for the final study visit should be performed at the time of discontinuation. In particular, patients are required to return the Cefaly® Abortive Program device.

[figure not shown]

Figure 1 - Study flowchart

# 5. Subjects

The study will include at least 60 men or women.

#### 5.1. Inclusion criteria

The following inclusion criteria apply:

- 1) Age from 18 to 65 years on the day of signing the informed consent form
- 2) ≥ 1-year history of migraine with or without aura according the diagnostic criteria listed in ICHD-III beta (2013) section 1, migraine (8), with the exception of aura without headache, hemiplegic migraine and brainstem aura migraine
- 3) Migraine onset before the age of 50 years
- 4) Having between 2 and 8 moderate or severe migraine attacks (Grade 2 or 3) per month in each of the two months prior to screening
- 5) Patient understands the study procedures, alternative treatments available, and voluntarily agrees to participate in the study by giving written informed consent
- 6) Patient is able to read and understand the written information (instruction sheet, paper diary and AE collecting form)

#### 5.2. Exclusion criteria

The following exclusion criteria apply:

- 1) Patient has difficulty distinguishing his/her migraine attacks from tension-type headaches
- 2) Patient has more than 15 headache days per month
- 3) Patient having received supraorbital nerve blocks in the prior 4 months
- 4) Patient having received Botox treatment in the prior 4 months
- 5) Modification of a migraine prophylaxis treatment in the previous 3 months
- 6) Diagnosis of other primary headache disorders, except rare (< 4) tension-type headaches per month
- 7) Diagnosis of secondary headache disorders included Medication Overuse Headache

- 8) Patients abusing opioids or user of recreational or illicit drugs or has had a recent history (within the last year) of drug or alcohol abuse or dependence
- 9) Implanted metallic or electronic device in the head
- 10) Cardiac pacemaker or implanted or wearable defibrillator
- 11) Patient having had a previous experience with the Cefaly® device
- 12) Migraine Aura without headache
- 13) Patient is currently participating or has participated in a study with an investigational compound or device within 30 days of screening visit (Visit 1)
- 14) Patients not having the ability to use appropriately the device and/or to perform themselves or bear the first 20-minute stimulation session during the training session at the study site

6. Medical device and treatment

